### 8.2.2 Laboratory Tests

For all continuous laboratory parameters, the lab values and change from baseline to post baseline visits are summarized by treatment group of A01 and overall and visit.

For all discrete laboratory parameters, the lab values are summarized with count and percentage by treatment group of A01 and overall and visit.

The lab tables will be generated for each Lab categories (Hematology, Biochemistry, Coagulation, Urinalysis and Hormones).

(Table 14.3.2.1, Table 14.3.2.2, Table 14.3.2.3, Table 14.3.2.4, Table 14.3.2.5)

All laboratory data will be listed with clinically relevant values flagged (L=Lower than lower limit of normal range or H=Higher than upper limit of normal range).

In addition, following clinical relevant ranges (and flags) will also be considered for summary table. The count and percent of subjects meeting the criteria will be presented. (Table 14.3.2.6)

- ALT  $\geq 3 \times$  Upper Limit of Normal Range (ULN), 5 $\times$  ULN, 8 $\times$  ULN, 10 $\times$  ULN
- AST and/or ALT  $\geq 3 \times$  ULN, 5 $\times$  ULN, 8 $\times$  ULN, 10 $\times$  ULN
- AST and/or ALT  $\geq 3 \times$  ULN with Total bilirubin  $\geq 2 \times$  ULN
- Total bilirubin  $\geq 2 \times$  ULN
- Creatinine  $\geq 2 \times$  ULN

The all clinical lab tests will be listed.

**Table 6 Routine Laboratory Tests**

Hematology:	
Hemoglobin	Mean corpuscular hemoglobin
Hematocrit	Mean corpuscular hemoglobin concentration
Platelet count	Mean corpuscular volume
Red blood cell count	White blood cell count and differential
Biochemistry:	
Alkaline phosphatase	Cholesterol
Aspartate aminotransferase	Triglycerides
Alanine aminotransferase	High density lipoprotein-cholesterol
Gamma-glutamyl transpeptidase	Low density lipoprotein-cholesterol
Potassium	Protein (total)
Sodium	Albumin
Chloride	Creatine kinase
Inorganic phosphate	Creatinine
Glucose	
Urea	
Bilirubin (direct and total)	
Coagulation:	
Prothrombin time	Activated partial thromboplastin time
International normalized ratio	
Urinalysis:	
Specific gravity, pH, protein, glucose, ketones, urobilinogen, blood	
Microscopic examination 	
Reproductive hormones	
Luteinizing hormone (LH)	
Follicle stimulating hormone (FSH)	
Estradiol (E2)	

 Performed only if required, based on urinalysis results.

### 8.2.3 Vital Signs

Vital signs data as below will be summarized descriptively in tables by treatment group of A01 and overall and scheduled visit (Table 14.3.3.1). All vital sign data will be listed.

- Sitting Systolic Blood Pressure (mmHg)
- Sitting Diastolic Blood Pressure (mmHg)
- Sitting Pulse Rate (bpm)
- Tympanic Body Temperature (°C)
- Body Weight (kg)

### 8.2.4 ECGs

ECG parameters as below values and changes from baseline will be summarized descriptively by treatment group of A01 and overall and scheduled visit. (Table 14.3.3.2.1)

- PR (msec)
- RR (msec)
- QRS (msec)
- QT (msec)

- QTcF (msec)
- QTcB (msec)

For ECGs, number and percentage of subjects meeting the criteria listed below will be presented in tables (Table 14.3.3.2.2):

- QTc > 500ms
- QTc > 480ms
- QTc > 450ms
- Change from baseline in QTc > 30 msec
- Change from baseline in QTc > 60 msec
- These criteria will be applied to both QTcB and QTcF.

Shift tables will present the changes in clinically relevant categories from baseline to EOT/Early discontinuation visit. The categories are; “QTcB<=450msec”, “QTcB >450 to <=480msec”, “QTcB >480 to <=500msec”, “QTcB >500msec”. (Table 14.3.3.2.3)

Similar shift table will be also created for QTcF. The categories are; “QTcF<=450msec”, “QTcF >450 to <=480msec”, “QTcF >480 to <=500msec”, “QTcF >500msec”. (Table 14.3.3.2.4)

All ECG parameters and findings will be listed.

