5.2.1.2 Visits 2 to 5 (Treatment period, Weeks 20, 28, 40, and 52)

Subjects will attend visits every 8 weeks between Visits 1 and 3 (Weeks 12, 20, and 28) and every 12 weeks between Visits 3 and 6 (Weeks 28, 40, 52, and 64). The following assessments will be performed (refer to Table 1 for further details):

- Physical examination (see Section 6.5.1)
- Body weight (Visit 4 only)
- Vital signs (including sitting blood pressure, pulse rate, and tympanic body temperature)
- 12-lead ECG (Visit 4 only)
- Routine laboratory evaluations (hematology, biochemistry, coagulation, and urinalysis)
- PHQ-8 and GAD7 (Visit 3 only)
- MENQOL (Visit 3 only)
- Review VMS diary (re-educate subject if necessary)
- Dispensing MT-8554 (Visits 2 to 5 only)
- Drug Accountability
- AE and concomitant medication recording.
- Diary compliance [REDACTED] reminder

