**Table 3 Derived Analysis Visit Windows**

Visit		Nominal day	Window
1	Week 12 (Baseline)	NA	NA
2	Week 20	Day 141	Day 113 to 169
3	Week 28	Day 197	Day 170 to 239
4	Week 40	Day 281	Day 240 to 323
5	Week 52	Day 365	Day 324 to 407
6	Week 64	Day 448	Day 408 to 462
7	Week 68 (FU)	Day 476	NA

The analysis visits are derived according to the following criteria:

- The unscheduled visits are not used for the deriving.
- If a study visit is the only one in an analysis window, this study visit becomes the derived analysis visit.
- If there are multiple visits in a visit window, the closest visit to the nominal day becomes the analysis visit. In the event that two visits are the closest visits to the nominal day and equally distanced to the nominal day, the visit after the nominal day becomes the derived visit.
- Unless otherwise specified, the baseline values are the last available assessment before the first dose of study A02.
- The follow-up visit will not be derived. The study visit will be used.
- Unscheduled visits and retests (same visit number assigned), will not be displayed in by-visit summary tables, but will be included in the data listings. All data will be listed. Listings will include treatment, scheduled, unscheduled, retest and early discontinuation data.
- The efficacy endpoints based on diary data use different windows. See Section 7.3.3.1.

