### 8.4 Dose Change

All subjects were treated with MT-8554 10 mg initially. Then from protocol amendment 4, all subjects remaining in study changed to MT-8554 5 mg. Some subjects already completed or discontinued the study. To compare the data before and after the dose change, the following analyses will be conducted.

No.	Title of Table	Analysis Population
14.1.5	Summary of Exposure to Study Medication: Duration of exposure the dose change	SAF
14.3.1.1	Summary of Treatment Emergent Adverse Events (TEAE)	SAF
14.3.1.1.Ex4Site	Summary of Treatment Emergent Adverse Events (TEAE -Exclude 4 Florida site-	SAF

No.	Title of Table	Analysis Population
14.3.1.2	Incidence of Treatment Emergent Adverse Events by System Organ Class, Preferred Term	SAF
14.3.1.2.Ex4Site	Incidence of Treatment Emergent Adverse Events by System Organ Class, Preferred Term -Exclude 4 Florida site-	SAF
14.3.1.4	Incidence of Treatment Emergent Adverse Events by System Organ Class, Preferred Term and Severity for before the dose change	SAF
14.3.6.1	Transvaginal Ultrasound (TVU)	SAF
14.3.6.1. Ex4Site	Transvaginal Ultrasound (TVU) -Exclude 4 Florida site-	SAF
14.3.6.2	Transvaginal Ultrasound (TVU) - Endometrial Thickness	SAF
14.3.6.2. Ex4Site	Transvaginal Ultrasound (TVU) - Endometrial Thickness -Exclude 4 Florida site-	SAF

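### The planned QTc tables do not determine how many women newly entered a higher QTc category at any time during A02

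*SAP*

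**What the plan says.** ECG parameters, including QTcF and QTcB, are among the primary safety endpoints (SAP 2.2.1). ECGs are scheduled at Visit 1 (Protocol 5.2.1.1), at Week 40 among the intermediate visits ("12-lead ECG (Visit 4 only", Protocol 5.2.1.2), and at Week 64 or early termination (Protocol 5.2.1.3).

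SAP 8.2.4 plans four ECG outputs:

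- **Table 14.3.3.2.1:** values and changes from baseline by scheduled visit.
- **Table 14.3.3.2.2:** "number and percentage of subjects meeting the criteria listed below will be presented in tables". The criteria are QTc above 450, 480 and 500 msec, plus two change rows, of which the first is "Change from baseline in QTc > 30 msec" and the second uses 60 msec. All apply to both corrections.
- **Table 14.3.3.2.3 (QTcB):** "Shift tables will present the changes in clinically relevant categories from baseline to EOT/Early discontinuation visit".
- **Table 14.3.3.2.4 (QTcF):** "Similar shift table will be also created for QTcF". No other time point is named.

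On baseline, SAP 7.2 says: "Unless otherwise specified, the baseline values are the last available assessment before the first dose of study A02". On dose, SAP 8.4 says that everyone began on 10 mg and adds: "Then from protocol amendment 4, all subjects remaining in study changed to MT-8554 5 mg". The table lists in SAP 8.4 and 8.5 contain no ECG output.

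**The concern.** A reader of the safety report will want to know how many women moved into a higher QTc category during the extension. One planned table conditions on baseline but looks only at EOT. The other may include Week 40 but does not condition on baseline. A woman at or below 450 msec at baseline, above it at Week 40 and back below it at EOT appears in the shift table as unchanged. In the cut-off table she cannot be told apart from a woman who was already above 450 msec at the A02 baseline. The change rows show the size of a rise, not the category reached.

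The dose change sharpens this. For a woman switched from 10 mg to 5 mg between Week 40 and EOT, Week 40 is her only scheduled post-baseline A02 ECG at 10 mg, and her EOT ECG is at 5 mg. The shift table then sets baseline against the later dose alone.

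**Working it through.** The plan states no figure to reproduce. The check is whether the planned tables, taken together, determine the number of new entries.

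**Step 1: a counter-example.** Take five women from one A01 group (QTc in msec). These are invented values, chosen only to test the tables.

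| Woman | Baseline | Week 40, set A | Week 40, set B | EOT, both sets |
|---|---|---|---|---|
| 1 | 455 | 445 | 445 | 440 |
| 2 | 435 | 445 | 435 | 440 |
| 3 | 435 | 440 | 440 | 440 |
| 4 | 445 | 435 | 455 | 440 |
| 5 | 455 | 455 | 445 | 440 |

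- Week 40 values, sorted: 435, 440, 445, 445, 455 in both sets.
- Changes to Week 40, sorted: -10, -10, 0, 5, 10 in both sets. So Table 14.3.3.2.1 is the same.
- Women above 450 msec after baseline: one in both sets, whether counted at Week 40 or at any time. Changes above 30 msec: none. So Table 14.3.3.2.2 is the same.
- EOT shift: two women move from above 450 to at or below it, and three stay at or below, in both sets.
- Women newly above 450 msec: none in A (woman 5 was already at 455), one in B (woman 4, from 445).

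Every planned table agrees and the answer differs.

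**Step 2: how wide the gap can be.** Let N be the number of women, K the number above 450 msec at any post-baseline ECG, and B the number above it at baseline. From K and B alone, new entries lie between max(0, K − B) and min(K, N − B). The documents give no QTc rates, so K and B are assumed.

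| N | K | B | New entries |
|---|---|---|---|
| 100 | 10 | 2 | 8 to 10 |
| 100 | 10 | 5 | 5 to 10 |
| 100 | 10 | 10 | 0 to 10 |
| 364 | 36 | 7 (2%) | 29 to 36 |
| 364 | 36 | 18 (5%) | 18 to 36 |
| 364 | 36 | 36 (10%) | 0 to 36 |

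The EOT shift table narrows these ranges, because a new entry still present at EOT is visible there. What stays open is a rise at Week 40 that had reversed by EOT, or one in a woman with no EOT ECG.

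**Step 3: what a highest-value shift does with no drug effect.** Assume QTcF with mean 420, between-woman SD 15 and within-woman SD 8 or 12 msec, independent within-woman noise, no drug effect, and 364 women. All of these means and SDs are assumptions. Expected crossings of 450 msec by simulation:

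| Within-woman SD | EOT shift, up / down | Highest-value shift, up / down |
|---|---|---|
| 8 | 7.8 / 7.8 | 13.4 / 5.5 |
| 12 | 14.3 / 14.3 | 25.2 / 10.8 |

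The EOT shift is balanced. The highest-value shift leans upward purely because it takes the larger of two readings.

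**The case against.** The strongest reply is that little is lost. Table 14.3.3.2.1 summarizes Week 40 values and changes, and SAP 6.1 requires minimum and maximum, so a scheduled Week 40 value above 480 or 500 msec would show. If no woman is above a cut-off at baseline and the count is at any time, the count equals the new entries. Under the Step 3 assumptions only 0.08 to 0.32 of 364 women exceed a QTcF of 480 msec at baseline, so the baseline problem hardly touches the higher QTcF cut-offs. Clinically significant ECG abnormalities are reported as AEs (Protocol 6.5.4), and all ECGs are listed. All of this stands and limits the gap mainly to 450 msec. It does not close it: the time basis is unstated, AE reporting depends on the investigator's judgement, and a hand count from listings is not a planned summary.

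Four stronger readings are tempting, and the documents do not support them:

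- **That the tables miss new prolongation at any time on MT-8554.** The A02 baseline precedes the first A02 dose, but A01 had 1, 5 and 10 mg arms (Protocol 3.3), so women from those arms may already be on drug at that baseline. The claim can cover A02 only.
- **That the cut-off counts overstate prolongation by including pre-existing values.** For the same women, a high A02 baseline may itself have arisen on drug.
- **That the EOT shift misses a large share of drug-related prolongation.** With no drug effect it shows 7.8/13.4 = 58% or 14.3/25.2 = 57% of the women newly above 450 msec at either ECG. The remainder there is measurement noise.
- **That a highest-value shift should replace the EOT shift at no cost.** Step 3 shows its upward bias, and A02 has no concurrent control against which to judge it.

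**Conclusion.** The point holds as a gap in the planned tables, not in the data collected. Followed exactly, SAP 8.2.4 leaves the number of new QTc category entries during A02 undetermined for a primary safety endpoint. This conclusion rests on the text and the counter-example, not on any assumed distribution. The gap is in effect one scheduled visit in the shift tables, plus a missing baseline split and time basis in the cut-off table. The actual number of women affected cannot be known from the documents. The bounds and the simulated counts rest on assumed rates, means and SDs, apply mainly to the 450 msec cut-off, and serve only as illustration. The consequence is greatest for women switched between Week 40 and EOT. This is a cheap improvement, not a defect that invalidates the ECG analysis.

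**What to change.** In SAP 8.2.4:

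1. Keep the EOT shift tables. Add to Tables 14.3.3.2.3 and 14.3.3.2.4 a second block from A02 baseline to each woman's highest post-baseline QTc, and state whether unscheduled ECGs count. SAP 7.2 keeps them out of by-visit tables but does not settle this case.
2. In Table 14.3.3.2.2, state that the counts are at any time after baseline. Keep the total row for each cut-off, and split it into women at or below the cut-off at A02 baseline and women already above it.
3. Show the split by A01 treatment group, with a note that the baseline in the active A01 arms may already be on drug.
4. Add a footnote to the new block: taking the highest value biases the shift upward even with no drug effect, there is no concurrent control, and the block must be read beside the EOT shift.

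The cost is SAP wording and minor programming on data already collected. The one real downside is the selection bias, which the footnote and the retained EOT shift address.

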### **8.2.5 Physical Examinations**

Physical examination data will be summarized descriptively in tables by treatment group of A01 and overall and visit (Table 14.3.4).

All physical examination data will be listed.

### **8.2.6 Breast Examination**

The breast examination data will be summarized in tables by treatment group of A01 and overall and visit (Table 14.3.5). All breast examination data will be listed.

### **8.2.7 Endometrial Safety**

All Endometrial safety data will be listed.

#### **8.2.7.1 Endometrial Thickness Measured by Transvaginal Ultrasound (TVU)**

The endometrial thickness as measured by TVU will be summarized in the tables by treatment group of A01 and overall and visit as below. (Table 14.3.6.1, Table 14.3.6.2)

1. Summary table presenting mean and SD for baseline, post baseline visits and change from baseline
2. Summary table of endometrial thickness by category (<5 mm, 5 to 8 mm, >8 mm)
3. Summary table for category of change from baseline (>3 mm, >5 mm)

The central reading data will be used for the analysis.

### 8.2.7.2 Endometrial Histology (Endometrial Biopsy)

The Endometrial biopsy data will be summarized in the tables by treatment group of A01 and overall and visit as below.

1. Summary tables of proportion of subjects in abnormal\* category (Table 14.3.7.1)
2. Shift table for change in abnormal category from baseline to week 64 or EOT(Table 14.3.7.2)

\*Note: The histological categories are based on 2003 draft FDA guidance. [REDACTED]

[REDACTED]

[REDACTED]

[REDACTED]

The data from adjudication committee will be used for the analysis.

### 8.2.8 Other Safety Assessments

Total score of 8-Item Patient Health Questionnaire (PHQ-8) and total score of the 7-item Generalized Anxiety Disorder questionnaire (GAD7) will be summarized descriptively in tables by treatment group of A01 and overall and scheduled visit. (Table 14.3.8, Table 14.3.9) The data listings will be generated.

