### 2.2 Study Endpoints

#### 2.2.1 Safety Endpoints (Primary Endpoints)

- Physical examination (including breast safety evaluation).
- Vital signs (blood pressure, pulse and tympanic body temperature).
- Electrocardiogram (ECG) parameters (including cardiac intervals: heart rate, PR, QRS, QT, QTcF and QTcB).
- Clinical laboratory assessments (hematology, biochemistry, coagulation and urinalysis).
- Reproductive hormones (luteinizing hormone [LH], follicle stimulating hormone [FSH], and estradiol [E2]).
- Adverse events (AEs).
- Endometrial safety (endometrial thickness as measured by transvaginal ultrasound, and incidence of endometrial hyperplasia as measured by endometrial biopsy).
- Breast safety (breast tenderness and incidence of breast cancer).
- Depression and anxiety as measured by 8-Item Patient Health Questionnaire (PHQ-8) and by Generalized Anxiety Disorder-7 (GAD7), respectively.

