## **6. GENERAL CONSIDERATIONS**

### **6.1 Descriptive Statistics**

Continuous data will be summarized descriptively using the number of observations, mean, standard deviation (SD), median, minimum and maximum. Categorical data will be summarized using frequency counts and percentages. The denominator for the percentages will be the total number of subjects in the treatment group and analysis population being presented, unless otherwise specified.

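### PHQ-8 and GAD7 are primary safety endpoints, but no planned table shows within-woman change or counts the women who worsen

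*SAP*

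**What the plan says.** SAP 2.2.1, headed "Safety Endpoints (Primary Endpoints"), lists nine items. The last is "Depression and anxiety as measured by 8-Item Patient Health Questionnaire (PHQ-8) and by Generalized Anxiety Disorder-7 (GAD7), respectively". Protocol 2.2.1 lists the same item among the safety endpoints that serve the primary objective.

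The whole analysis of the two questionnaires is in SAP 8.2.8. The total scores "will be summarized descriptively in tables by treatment group of A01 and overall and scheduled visit. (Table 14.3.8, Table 14.3.9"), followed by "The data listings will be generated". Protocol 10.3.4 asks only for tables suited to the data type, with graphs and listings as needed, and leaves further detail to the SAP.

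Two general rules fill this in. SAP 6.1: "Continuous data will be summarized descriptively using the number of observations, mean, standard deviation (SD), median, minimum and maximum". SAP 7.2: "Listings will include treatment, scheduled, unscheduled, retest and early discontinuation data".

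For several other measures the SAP goes further. For continuous laboratory parameters, "the lab values and change from baseline to post baseline visits are summarized" (SAP 8.2.2), and women beyond liver and creatinine limits are counted. For ECG there are QTc threshold counts, and "Shift tables will present the changes in clinically relevant categories from baseline to EOT/Early discontinuation visit" (SAP 8.2.4).

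**The concern.** The safety question for a mood questionnaire is whether some women become clearly more depressed or anxious on the drug, and how many. That concerns change within a woman and the tail of the distribution. By-visit statistics of the total score describe who answered at each visit. They do not link a woman's later score to her own baseline.

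The sample also shrinks. Up to 364 women may enrol, and the study ends when about 100 have completed (Protocol 4.1). The questionnaires are due only at Week 12, Week 28 and Week 64 or early termination (Protocol 5.2.1), and SAP 7.1 uses observed data only. A visit mean can therefore move because different women answer. At stake is whether the report can state a worsening rate for a primary safety endpoint, or must leave the reader to count from listings with a cut-off chosen after seeing the data.

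**Working it through.** **1. What each measure gets in the SAP**

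| Measure (SAP section) | Status | Change from baseline | Category, threshold or shift |
|---|---|---|---|
| PHQ-8, GAD7 (8.2.8) | primary safety | none named | none named |
| Laboratory (8.2.2) | primary safety | yes | yes |
| ECG (8.2.4) | primary safety | yes | yes, for QTc |
| Endometrial thickness (8.2.7.1) | primary safety | yes | yes |
| Endometrial biopsy (8.2.7.2) | primary safety | shift from baseline | yes |
| Vital signs (8.2.3) | primary safety | none named | none named |
| VMS frequency and severity, MENQOL (8.3) | exploratory | yes | none named |

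**2. Plan figure to reproduce.** There is none. SAP 3.3 states that there is no formal sample size estimation. The documents give no SD for the scores and no size of worsening that matters, so steps 3 to 6 are illustrations on assumed values: 3 or 5 women worsening, rises of 5, 10 or 15 points, and SD of 3 to 5 points. N = 100 and N = 364 come from Protocol 4.1.

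**3. Shift in the mean.** If k women rise by d points and nobody else changes, the shift is k × d / N.
- 5 women, 10 points, N = 100: 50/100 = 0.50. For 5 and 15 points: 0.25 and 0.75.
- 3 women, N = 100: 0.15, 0.30 and 0.45 for rises of 5, 10 and 15 points.
- 5 women, 10 points, N = 364: 50/364 = 0.14.
- 5 of 100 rise by 10 and the other 95 fall by 0.5: (50 − 47.5)/100 = 0.025.

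The 95% half-width for a mean is 1.96 × SD/√N. At N = 100 it is 0.59, 0.78 or 0.98 for SD 3, 4 or 5, so a shift of 0.50 lies inside it.

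**4. Shift in the SD.** If the 5 in 100 are typical at baseline, the new SD is √(SD² + 0.05 × 0.95 × 10²) = √(SD² + 4.75). SD 3, 4 and 5 become 3.71, 4.56 and 5.45. This is a modest rise with no unique reading.

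**5. Shift in the maximum.** It rises only if a worsened woman passes the highest score already present. In a simulation (100 women, negative binomial scores with mean 3 capped at an assumed 24, 5 random women rising by 10, 20,000 runs), the maximum did not rise in 35%, 70% and 87% of runs for SD 3, 4 and 5. These shares depend on the assumed distribution.

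**6. What a count would show.** 5 of 100 is 5.0% (Clopper-Pearson 95% CI 1.6 to 11.3%), and 3 of 100 is 3.0% (0.6 to 8.5%).

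**7. Where early end-of-treatment forms land.** SAP Table 3 assigns visits by study day: Week 20 is Days 113–169 (57 days), Week 28 is 170–239 (70), Week 40 is 240–323 (84), Week 52 is 324–407 (84) and Week 64 is 408–462 (55), 350 days in all. Neither questionnaire is scheduled at Weeks 20, 40 or 52, whose windows cover 57 + 84 + 84 = 225 of the 350 days (64%). An early form on Day 300, for example, falls in Week 40. SAP 8.2.8 does not say whether a by-visit table would show it. The ECG shift tables avoid the question by naming the early discontinuation visit.

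**The case against.** A reader might infer that only means are reported, that deterioration would go unseen, and that women who leave because they worsen disappear from the data. The documents do not support any of these.

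- SAP 6.1 adds SD, median, minimum and maximum.
- Listings are planned, ordered by subject and visit (SAP 9.1), and include early-discontinuation data. With up to 364 women and at most three scheduled forms each, a marked rise can be found.
- Women who withdraw early should have the end-of-treatment visit (Protocol Table 1, note 4), which includes both questionnaires (Protocol 5.2.1.3). Women who stop treatment are encouraged to stay in the study (Protocol 4.5.1).
- Adverse events are sought by open questions at each visit (Protocol 8), and those reported in the calls at least every 4 weeks are documented (Protocol 5.2.4). Mood events so reported are tabulated (SAP 8.2.1). Part of that table list is redacted, so the full set cannot be seen.
- Vital signs get the same plain treatment, so the questionnaires are not alone. SAP 8.2.8 also meets what Protocol 10.3.4 asks, so there is no contradiction between the documents.

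All of this stands, and it limits the point to missing quantification. It does not remove it. The added statistics are still per visit and not within-woman. Listings yield no rate, and laboratory and ECG data are listed too yet are also counted. Clinically significant vital-sign, ECG and laboratory abnormalities must be reported as adverse events (Protocol 6.5.3, 6.5.4 and 6.5.7), but Protocol 6.6 has no such rule for a worsened PHQ-8 or GAD7 score, so it need not reach the adverse event tables.

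**Conclusion.** The point holds as a gap in quantification. Worsening on PHQ-8 or GAD7 would be visible in the listings, but no named table would measure it within women or count it. Early end-of-treatment forms may be left out of the by-visit rows; the SAP is silent here, so this is a possibility and not a stated exclusion.

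The comparison of plans in step 1 and the window arithmetic in step 7 rest on the documents alone. The size figures (a 0.5-point shift in the mean against a 5.0% count) rest on assumed numbers of women, rises and SDs. They show how little the planned statistics could move and do not predict what will happen. The change is worth making because these are primary safety endpoints and the SAP already uses such displays for comparable measures. It does not undermine the rest of the safety analysis.

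**What to change.** In SAP 8.2.8, for each instrument, by A01 group and overall, add:

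1. Change from A02 baseline in total score by visit, with the SAP 6.1 statistics.
2. Either a shift table from baseline to worst post-baseline category, or the number and percentage of women whose worst post-baseline score exceeds baseline by a set amount. The denominator is women with a baseline and at least one post-baseline form. Early end-of-treatment forms count, whichever window they fall in.

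The sponsor should justify the categories or cut-off and fix them before database lock; the documents supply none.

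The cost is two short tables from data already collected, with no protocol change. Two limits remain: the rate is uncontrolled and cannot by itself establish causation, and women with no post-baseline form still cannot be counted, so their number should be shown beside the table.
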